2. FUNDING

The study is physician-sponsored. The medical device to perform endovascular exclusion of the AAA will be provided by the national health system. The clinical workup, hospitalization, and operation costs will be delivered under the national health system without any additional cost compared to standard care. A specific insurance for the patients being part of the study will not be required.

4. BACKGROUND

Endovascular aneurysm repair (EVAR) is currently the preferred choice to treat the abdominal aortic aneurysms (AAA) with a feasible anatomy^{1,2}. However, approximately 40-60% of AAA patients presented unfavorable characteristics for EVAR, mainly due to a “hostile neck anatomy”³⁻⁵. In “real-world” clinical practice, up to 44% of EVAR cases are performed outside Instruction For Use (IFU) for an adverse neck anatomy⁶. Short (<15-mm), angulated (>60°), and wide (>28-mm) aortic necks are the main features concurring to the proximal HNA⁶.

The recourse to standard EVAR is currently routine for patients who are not eligible for OR, with acceptable short- and mid-term outcomes, but the long-term durability of EVAR depends on maintaining proper sealing between the endograft and the aortic neck as well as the iliac arteries⁷. HNAs demonstrated worse results when compared to “favorable” ones in terms of technical success (94% vs. 98%) and type-Ia endoleak rate (10% vs. 2%).⁶ The issue linked to an unfavorable anatomy can be addressed with more complex techniques, but these are limited by high production costs and considerable complexity.⁸⁻⁹

TREO (Terumo Aortic, Inchinnan, Renfrewshire, UK; formerly Treovance, Bolton Medical, Sunrise, Fla) is a standard bifurcated, modular stent-graft that has shown compelling early- and mid-term results¹⁰⁻¹¹. It seems clear that several physicians are still looking for a feasible solution for HNA patients to keep the complexity of the procedure comparable to standard EVAR while yielding improved results.

Moreover, there is a lack of publications addressing the issue of mismatched take-off of the renal arteries (RAs). This morphology seems to influence the sealing length and could justify

the introduction of dedicated devices. A recent study from our group currently under review for publication demonstrated that 25% of patients eligible for EVAR presented with mismatched RAs and that a dedicated device could improve sealing significantly. The study group sealing zone's length increased by about 25% when applying a hypothetical prototype with a single 10x10mm (wide x high) renal scallop. The same approach could be applied to the sealing surface with similar results.

The present study aims to evaluate the clinical effectiveness of an off-the-shelf standardized single renal scalloped stent-graft (Treo, Terumo Aortic) to treat infrarenal AAA. The final objective will be to employ the data obtained in this cohort for a future eventual development of an "off-the-shelf" device dedicated to patients with mismatched renal arteries. Such an endograft could keep the complexity of the procedure as similar as possible to standard EVAR while improving sealing.

5. STUDY AIM

BASIC RESEARCH

To evaluate the clinical effectiveness of EVAR with an “off-the-shelf” single-renal-scallop endograft (TREO, Terumo Aortic) in the treatment of AAA patients with mismatched renal arteries. These data will be used to evaluate the clinical advantages of the adoption of a dedicated device for this kind of patients. See the protocol below for methods.

CLINICAL STUDY

To assess the real-world, in-vivo, clinical effectiveness of the use of a single-renal scallop endograft to treat infrarenal AAA. The study population is subjects with infrarenal AAA eligible for EVAR, of both sexes, aged 18>years, and with mismatched renal arteries. The mismatch was defined by a distance between the takeoff of the two proper renal arteries \geq of 10mm. The study group is intended for patients receiving EVAR with the pre-mentioned dedicated custom-made endograft (from now called Prototype). The clinical intervention will be performed in the study participating centers and for our competence at the Unit of Vascular Surgery (Ospedale Civile di Baggiovara, Azienda Ospedaliero-Universitaria di Modena, [name]).

Expected results and risk/benefit considerations

The results will demonstrate whether the “Prototype” is effective for the treatment of AAA with mismatched RAs. The effectiveness will be evaluated in terms of technical and clinical

success. Other objectives are the evaluation of procedure-related adverse events and re-interventions, as well as operative details.

The use of fenestrated and branched endograft has already been demonstrated to be safe and feasible for the treatment of HNA AAA¹³⁻¹⁴. However, the complexity of the repair, the high costs, and the significant risk of renal and neurological injury limited the widespread of these techniques^{8,9, 15}. On the other hand, standard EVAR has been used in HNA AAA with acceptable results in short- and mid-term period¹¹⁻¹². The actual challenge is to improve the outcomes of patients with unfavorable anatomy for standard EVAR keeping the complexity as low as possible.

Literature evaluating the mismatch of renal arteries in AAA patients is lacking and a recent study carried out in our unit demonstrated that about one-third of these presented an infrarenal distance of more than 10mm. These particular anatomical characteristics seem to influence the length of sealing and justify the evaluation of a dedicated device.

The benefits could be relevant for the patients in terms of reduction of procedure-related adverse events such as endoleaks and related re-interventions. Furthermore, the use of custom-made standardized devices could produce a significant reduction in costs for health care providers and in the future, it could be the base for an “off-the-shelf” endograft. Procedure-related complications were expected to be similar to standard EVAR and reduced in comparison with literature reporting adverse events in more complex techniques. To confirm this forecast all adverse events will be reported in our CRF and prospectively monitored. Moreover, complications directly imputable to device defects will be promptly communicated to the regulatory authority and managed following law dispositions.

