6. STUDY DESIGN

This study is a multi-center non-randomized prospective observational post-marketing cohort study. The cohort of patients will be followed up for a minimum of 5 years after the treatment.

The study aimed to test the EVAR with the “prototype” device in mismatched renal arteries AAA.

Inclusion/exclusion criteria were reported above.

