Adverse events are defined as any systemic or local complication directly related to the procedure. Adverse events that occurred in the first 30-day were considered procedure-related, unless differently demonstrated.

Any surgical, open, or endovascular, procedure aimed to address adverse events was named re-intervention.

The secondary endpoints represent specific technical aspects related to the procedure and the endograft.

Treatment-related adverse events and re-interventions are important to state the safety of the procedure over time and its external reproducibility.

The procedure and fluoroscopy time, as well as the contrast-medium dose, will be used to evaluate the complexity of the procedure, comparing it with the same reported in the literature for standard EVAR.

Timeline

[figure not shown]
Months 1-3 Organization and logistic set-up.

Months 3-15 Subjects enrollment, data collection, treatments, clinical follow-up.

Months 15-18 Conclusion of recruitment, first (3 months) follow-up end for every patient, ad-interim analysis

Month 27-39 2-year follow-up end, mid-term analysis

Month 63-75 Conclusion of the follow-up, analysis of the results and their validation,

statistical analysis, project completion and analysis for further work, dissemination of the results

Gantt chart:

Sample size

No statistical analysis of the sample size was carried out. Considering the number of AAA responding to the inclusion criteria treated in the participating centers and the enrollment period (1 year) a sample size of 50 patients was estimated. This number should be sufficient to evaluate the endpoints reported in the appropriate section.

The estimated number of patients recruited for the present center is 15 patients

Recruitment

All the involved centers represent the third referral level of complex Abdominal Aortic Aneurysms.

For what concerns our center all patients affected by AAA responding criteria for treatment were evaluated at the Vascular Surgery Unit of the Azienda Ospedaliero Universitaria di Modena. Those meeting the inclusion criteria will be singularly recruited.

Taking into account a mean of 120 endovascular procedures on the abdominal aortic and 10 complex procedures with custom-made devices, a safety 12-month recruitment should be considered. The entire Medical staff of the department is informed about the present project and will refer the potential subjects to the Investigators.

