Continuous variables will be expressed as mean, and standard deviation, and differences tested with the two-sided t-test or the Mann–Whitney U-test, if appropriate. Categorical variables will be expressed as counts and percentages and the chi-square test or Fisher's exact test will be used for analysis. All data will be entered into the logistic regression model if they had a univariable P-value of <0.05 . Data resulting significant in this model will be put in a multivariate one. In the multivariable analyses, clinical factors or potential confounding variables will be expressed as odds ratios with 95% confidence interval (CI). The goodness of fit of the logistic regression models will have been assessed by calculating the C-statistic. Survival analysis and freedom from adverse events will be assessed through the Kaplan-Meier analysis with their relative 95% CI. A P-value < 0.05 defined the statistical significance. The analysis was carried out using STATA 15.1 (StataCorp College Station, Texas, USA).

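### The cohort contains only scalloped-graft recipients, so it can estimate absolute success but cannot show a clinical advantage over standard EVAR or confirm similarity to it

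*Combined protocol and SAP*

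**What the plan says.** The combined protocol and SAP describes one treated group.

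- **Design (section 6):** "This study is a multi-center non-randomized prospective observational post-marketing cohort study".
- **Who is studied (section 5):** "The study group is intended for patients receiving EVAR with the pre-mentioned dedicated custom-made endograft (from now called Prototype"). No second group is defined anywhere.
- **Comparative aim (section 5):** "These data will be used to evaluate the clinical advantages of the adoption of a dedicated device for this kind of patients".
- **Expected benefit (section 5, expected results):** patients could gain through "reduction of procedure-related adverse events such as endoleaks and related re-interventions". Complications are forecast to be similar to standard EVAR, and adverse events are collected in order to confirm that forecast.
- **Complexity (section 7, Endpoints):** procedure time, fluoroscopy time and contrast dose are to be assessed by "comparing it with the same reported in the literature for standard EVAR". No paper, benchmark value, margin or method is given.
- **Eligibility (section 7):** anatomy must lie inside the standard TREO IFU, with an inter-renal distance of at least 10 mm.
- **Sample size (section 7):** 50, from expected accrual over one year, with no statistical calculation.
- **Available evidence (sections 4 and 5):** the protocol itself says that literature on mismatched renal arteries is lacking.

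**The concern.** An advantage, a reduction and a similarity are all statements about a difference between two treatments, and the study observes one. The eligibility rule sharpens the problem. Because every patient is also inside the standard graft's IFU, good outcomes are plausible with the unscalloped device too. A scallop that adds nothing and a scallop that helps could give the same single-cohort result.

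For complexity, a comparison with papers chosen after the data are in mixes the device effect with differences in centre, operator and case mix. Added time from aligning the scallop could look large or negligible depending on which paper is used.

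At stake is what the study may conclude. Section 4 says the data are meant to inform development of a dedicated device, so an unsupported statement of advantage would carry weight.

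**Working it through.** The plan has no power or precision figure to reproduce: 50 is an accrual estimate. The checks below ask what 50 patients can show.

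**Inputs.** n = 50 (section 7, Sample size). The only outcome rates in the documents are in section 4, for hostile versus favourable necks: type Ia endoleak 10% v 2%, technical success 94% v 98%. These are not rates for mismatched renal arteries or for scallop versus standard graft. They are used here only as an assumed range.

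**1. What a scallop with no effect would show.** Let p be the standard graft's type Ia rate in these patients.
- At p = 0.02: P(0) = 0.98^50 = 0.364; P(1) = 50 × 0.02 × 0.98^49 = 0.372; P(0 or 1) = 0.736.
- At p = 0.10: P(0 or 1) = 0.034.

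So 0 or 1 leak in 50 is the expected result without any benefit if the true background is 2%, and would be surprising if it is 10%. The documents do not say which applies to this anatomy.

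**2. Precision of the single cohort (exact Clopper-Pearson 95% limits).**
- 1 leak in 50: 0.05% to 10.6%, which includes both 2% and 10%.
- 0 leaks in 50: upper limit 1 − 0.025^(1/50) = 7.1%.
- 49/50 technical successes: 89.4% to 99.9%, which includes both 94% and 98%.
- 50/50 technical successes: lower limit 0.025^(1/50) = 92.9%, still below 94%.

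These are legitimate estimates of absolute performance. They do not separate the device from its background.

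**3. Whether an added comparator would rescue the claim.** Take 50 Prototype v 50 unscalloped, two-sided alpha 0.05, with p̄ the mean of p1 and p2:

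Power = Φ{ (|p1 − p2|√n − 1.96√[2p̄(1 − p̄)]) / √[p1(1 − p1) + p2(1 − p2)] }

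- Endoleak 10% v 2%: (0.08 × 7.071 − 0.658)/0.331 = −0.280, so power is 39% (19% with Fisher's exact test). For 80% power, n per group = [(0.658 + 0.279)/0.08]² ≈ 137.2, so 138.
- Technical success 94% v 98%: (0.04 × 7.071 − 0.543)/0.276 = −0.944, so power is 17% (3% with Fisher's exact test). For 80% power, n per group = [(0.543 + 0.232)/0.04]² ≈ 375.6, so 376.
- Continuous measure such as procedure time: unadjusted 95% half-width = 1.96 × √(1/50 + 1/50) = 0.39 SD.

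A comparator of that size would be usable for procedure measures and not for clinical advantage.

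**The case against.** The strongest reply is that the operative objective is absolute. Section 5 asks whether the Prototype is effective, judged by technical and clinical success, and one cohort can estimate that. Complexity is only a secondary endpoint, and the benefit statement is conditional. This stands: the defect lies in the comparative statements, not in the primary endpoint or the study as a whole.

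Three stronger readings are tempting, and the documents do not support them.

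- **That the planned tests cannot be used.** A reader might infer this from section 8, where "differences tested with the two-sided t-test" appears without a second group. The tests also serve as the univariable screen for the risk-factor model. Against published data, a t-test needs only mean, SD and n, and chi-square or Fisher's test needs only counts. Only the rank test needs individual values. The difficulty with the literature comparison is confounding and the unnamed source, not computability.
- **That a pool of comparable patients goes unrecorded.** Section 7 gives "Taking into account a mean of 120 endovascular procedures on the abdominal aortic" and section 4 reports that "25% of patients eligible for EVAR presented with mismatched RAs" (about one-third in section 5). One could compute 120 × 0.25 = 30 to 120/3 = 40, less 15 planned recruits, leaving 15 to 25 a year. But no time unit is attached to the 120, and the sum ignores the exclusions for symptomatic or small aneurysms, anatomy outside the IFU, and refusal. The sample size was itself based on the number meeting the criteria, which may leave few or none.
- **That adding a control group would license the claim of advantage.** At 39% and 17% power it would not. Patients given the unscalloped graft may also have been chosen because it suited them.

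**Conclusion.** The point holds for the comparative claims. The study can report absolute technical and clinical success with confidence intervals. It cannot attribute good results to the scallop, show fewer endoleaks or re-interventions than standard EVAR, or confirm similar complications. The planned literature comparison gives weak descriptive context for complexity; it is not absent, but as written it has no fixed benchmark.

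On size: with an assumed 2% background type Ia rate, an ineffective scallop gives 0 or 1 leak in 50 about 74% of the time (3% if the background were 10%), and 1/50 carries a 95% CI of about 0.05% to 10.6%. Both background rates are borrowed from general neck anatomy. The structural conclusion, that one group cannot yield a contrast, does not depend on them.

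A reader might go further and conclude that nothing about the device can be learned, or that a control cohort is essential. Neither follows. The primary endpoint is estimable, and limiting the conclusions resolves the problem.

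**What to change.** **Recommended.**
1. In section 5 (aim and expected results), restate the purpose as feasibility, safety and estimated technical and clinical success, each with a 95% CI.
2. Remove the statements that the data will evaluate clinical advantages and will confirm similarity to standard EVAR.
3. In section 7 (Endpoints), label the literature comparison as descriptive, and name the source papers and benchmark values before the data are analysed.

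The cost is wording plus a short literature selection. Under section 10, protocol changes go to the ethics committee.

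**Optional.** The centres' routine records may hold elective patients with inter-renal distance of at least 10 mm, inside the TREO IFU, who received the unscalloped graft, concurrently or earlier. If so, report differences in procedure time, fluoroscopy time and contrast dose with 95% CIs, adjusted for neck length and centre if numbers allow. The documents do not give the number of such patients. The ±0.39 SD above needs 50 of them and is before adjustment. The comparison would be non-randomised and open to confounding by indication, would need ethics committee approval for data on non-enrolled patients, and would be too small to support a claim on endoleak or technical success.

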Primary endpoint: Clinical effectiveness measured in terms of technical and clinical success.

Technical success was defined as defined on an intent-to-treat basis and requires the successful introduction and deployment of the device in the absence of surgical conversion or mortality, type I or III endoleaks, or graft limb obstruction. A technical success thus implies the following qualifying details: 1. Successful access to the arterial system using a remote site (ie, the femoral, external iliac, common iliac, or brachiocephalic arteries with or without the use of a temporary or permanent prosthetic conduit to access these arteries); 2. successful deployment of the endoluminal graft with secure proximal and distal fixation; 3. absence of either a type I or III endoleak; 4. patent endoluminal graft without significant twist, kinks, or obstruction (>30% luminal stenosis or a pressure gradient >10 mm Hg) by intraoperative measurements; 5 patency of both renal arteries and at least one hypogastric artery. Primary technical success can include the use of additional modular components, stents, angioplasty, and adjunctive surgical procedures. However, if unplanned endovascular or surgical procedures are necessitated it must be noted.

Clinical success requires the successful deployment of the endovascular device at the intended location without death as a result of aneurysm-related treatment, type I or III endoleak, graft infection or thrombosis, aneurysm expansion (diameter >5 mm, or volume >5%), aneurysm rupture, or conversion to open repair, occlusion of the renal arteries. The clinical success was measured at every follow-up interval. Any additional maneuvers, planned or unplanned, aimed to maintain clinical success must be carefully reported.

Secondary endpoints:

- Evaluation of the intra-operative and peri-operative (within 30 days) adverse events

- Collection of eventual adverse events related to the treatment procedure and eventual post-hoc analysis
- Evaluation of reintervention (time elapsed since index operation, type, and indication);
- Evaluation of potential risk factors (baseline, anatomical features, procedural technique) potentially related to adverse events
- Evaluation of the main procedural and fluoroscopy time, evaluation of the average contrast medium (CM) dose as well as Dose Area Product (DAP) (mGym3).

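### The protocol promises a verdict on whether the Prototype is effective, but sets no benchmark, no test of a success rate and no deciding visit for clinical success

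*Combined protocol and SAP*

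**What the plan says.** Section 5 (Study aim, expected results) commits to an answer: "The results will demonstrate whether the “Prototype” is effective for the treatment of AAA with mismatched RAs". Section 6 (Study design) likewise describes the purpose as testing repair with this device, while classing the study as follows: "This study is a multi-center non-randomized prospective observational post-marketing cohort study". The Background intends the data to inform later development of a dedicated off-the-shelf graft.

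Section 7 (Endpoints) gives one primary endpoint with two components: "Primary endpoint: Clinical effectiveness measured in terms of technical and clinical success". Success is defined in detail for the individual patient. Technical success concerns the index procedure. For the other component, "The clinical success was measured at every follow-up interval". The Timeline schedules three analyses, at months 15-18, 27-39 and 63-75.

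On size, Section 7 says "No statistical analysis of the sample size was carried out". From centre volume and a one-year enrolment period "a sample size of 50 patients was estimated", followed by the assurance "This number should be sufficient to evaluate the endpoints reported in the appropriate section".

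Section 8 (Statistical methods) lists tests of differences between groups, logistic regression and Kaplan-Meier curves, and adds: "A P-value < 0.05 defined the statistical significance".

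**The concern.** A study that is to show whether a device is effective needs a result that would count as yes and a result that would count as no. Here the individual outcomes are defined but the cohort-level criterion is not. Everyone in the study group receives the Prototype, so the between-group tests have no comparator treatment for the primary endpoint, and no external rate is adopted in its place. The only literature comparison planned in Section 7 is for procedure time, fluoroscopy time and contrast dose.

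A report that called the device effective would therefore rest on a pass mark, a visit and a way of combining the components that were all picked once the results were known. The error rate of that conclusion would be unknown, although it is meant to inform development of a new device.

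**Working it through.** **Step 1. The plan's own figure.** The only design figure is N = 50. It cannot be reproduced or refuted, because it comes from feasibility and the plan gives no power, null rate, target rate or margin. For the same reason no pass mark can be inferred from it.

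**Step 2. What a verdict needs, against what is written.**

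| Element | In the plan |
|---|---|
| Benchmark or floor, technical success | None (94% and 98% appear in the Background only) |
| Benchmark or floor, clinical success | None |
| Test of a success rate against a benchmark | None in Section 8 |
| Significance level | 0.05, general; not attached to such a test |
| Sidedness | Two-sided, stated for the t-test only |
| Rule combining the two components | None |
| Time point, technical success | Tied to the index procedure |
| Deciding visit, clinical success | None; all intervals, three analyses |

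**Step 3. Effect of an open pass mark.** With n = 50 and pass mark r, the chance of passing is P(X ≥ r) = Σ from x = r to 50 of C(50, x) p^x (1−p)^(50−x). Take p = 0.90 as an assumed true rate:

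| Mark | ≥45 | ≥47 | ≥48 | ≥49 | 50 |
|---|---|---|---|---|---|
| P(pass) | 61.6% | 25.0% | 11.2% | 3.4% | 0.5% |

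**Step 4. What 50 patients can show.** The Clopper-Pearson two-sided 95% limits are L = Beta quantile(0.025; x, 51−x) and U = Beta quantile(0.975; x+1, 50−x). For x = 50, L = 0.025^(1/50) = 92.9%.

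| x/50 | Two-sided 95% interval | One-sided 95% lower limit |
|---|---|---|
| 42 | 70.9–92.8% | 73.0% |
| 45 | 78.2–96.7% | 80.1% |
| 46 | 80.8–97.8% | 82.6% |
| 47 | 83.5–98.8% | 85.2% |
| 48 | 86.3–99.5% | 87.9% |
| 49 | 89.4–99.9% | 90.9% |
| 50 | 92.9–100% | 94.2% |

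If the lower two-sided limit had to exceed an illustrative floor, the rules would behave as follows:

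| Floor | Needs | P(pass) if truth = floor | if 94% | if 98% |
|---|---|---|---|---|
| 80% | ≥46 | 1.8% | 82.1% | 99.7% |
| 85% | ≥48 | 1.4% | 41.6% | 92.2% |
| 90% | 50 | 0.5% | 4.5% | 36.4% |

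**Step 5. The 94% in the Background.** With a two-sided 95% interval no result from 50 patients shows a rate above 94%, since 50/50 reaches only 92.9%. At one-sided 0.05, 50/50 does, because 0.05^(1/50) = 94.2%; the corresponding false-pass rate is 0.94^50 = 4.5%. In the other direction, 42/50 or fewer shows a rate below 94% (upper limit 92.8%).

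**Step 6. Clinical success.** The documents give no loss rate. As an illustration only, 36/40 evaluable gives 76.3–97.2% and 40/45 gives 75.9–96.3%, so a count fixed for 50 patients would not carry over to a later visit. The visit itself is also unsettled. The inclusion criteria list CT angiography at 3 months, 12-18 months and 5 years, with clinical and ultrasound visits at 6, 12 and 36 months and yearly after that. The Follow-up text has CT angiography within 3 months and then every year for 5 years. The mid-term analysis is keyed to 2 years, for which the inclusion-criteria list has no visit.

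**The case against.** The strongest reply is that this is an observational post-marketing cohort. Its main aims are phrased as evaluating and assessing, the disputed sentence sits in a narrative on expected results, and the sample-size paragraph is open about having no calculation. An estimation study needs no pass mark. All of this stands, and it is why rewording is preferred to imposing a formal test. It does not rescue the present text, because Section 5 still promises a verdict and Section 6 still speaks of testing. A confidence interval with no reference value cannot deliver either.

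A reader might also infer more than the documents support:

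- *That no significance level exists.* Section 8 states one; it is simply not linked to a test of either success rate.
- *That neither component has a time point.* Technical success is tied to the procedure; only clinical success lacks a deciding visit.
- *That the plan is built to declare success, or that nearly any result would pass.* Without a rule the plan can formally return neither verdict. The defect is an undefined conclusion, not one slanted by design.
- *That 50 patients can never exclude 94%.* Step 5 shows this depends on direction and sidedness. The 94% also describes hostile-neck repair, whereas this study admits only anatomy within the device's instructions for use.

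**Conclusion.** The concern holds in this form: the plan claims a conclusion that its design and analysis cannot produce. The data would remain usable for estimation, so this is a fault in the stated claim rather than in the cohort.

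Its size is the spread in Step 3: the same device would pass with probability 61.6% or 11.2% depending on whether the mark is set at 45 or 48 of 50. Those figures assume a true rate of 90% and 50 evaluable patients. The 80%, 85% and 90% floors are illustrations, not values from the documents. The figures bear on a single proportion; no magnitude can be given for clinical success without a named visit and an evaluable number. The absence of a benchmark, a linked test, a combining rule and a deciding visit rests on the text alone and needs no assumption.

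**What to change.** **Preferred.** In Sections 5 and 6, replace the promise to demonstrate effectiveness and the reference to testing with wording such as: *The study will estimate the technical success rate, and the clinical success rate at [one named primary visit], each with an exact two-sided 95% Clopper-Pearson interval. Clinical success at other visits is descriptive. No conclusion on effectiveness will be drawn from a pass mark.* Carry the same analysis into Section 8. Before naming the visit, reconcile the schedules in the inclusion criteria and in the Follow-up text so that the visit exists for every patient.

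**Alternative, if a verdict is wanted.** Before any outcomes are reviewed, state a justified floor for each component, the alpha and its sidedness, the deciding visit for clinical success, and that both components must pass. Apply the rule to the interval limit at the actual evaluable number, not to a fixed count. Step 4 shows what each floor would demand at 50 patients. Any statement about the 94% must give its sidedness and the population it came from.

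**Cost.** Either route needs protocol wording plus the schedule reconciliation, with no extra patients. The downside is real: the study makes a weaker claim, or it can fail its own mark.
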